2.1 Background Information and Relevant Literature

The goal of this open-label pilot study is to establish the feasibility of a program of remotely supervised transcranial direct current stimulation (RS-tDCS) paired with word naming practice for people living with the semantic or logopenic variants of primary progressive aphasia (PPA). We will also collect preliminary efficacy data for speech and language outcomes following treatment. These data will be used to inform a grant application to complete the next step of a randomized controlled trial.

Primary Progressive Aphasia (PPA) is a neurological condition associated with a gradual progressive decline in language function, affecting three in 100,000 people annually¹, which is a conservative estimate.

PPA is a devastating language-led neurodegenerative syndrome that is associated with atrophy of predominately left-hemisphere brain regions governing language. The three variants of PPA – semantic, logopenic, and nonfluent/agrammatic – are characterized by distinct neural areas of atrophy including frontal, temporal, and parietal regions^{2,3}. The semantic variant is characterized by word knowledge loss; the logopenic variant by difficulties in word retrieval and repetition that are primarily phonologically mediated, and the nonfluent/agrammatic variant is differentiated by impairment in syntax and motor speech⁴. Beyond the devastating impact that PPA has on language, individuals living with PPA are often middle-aged when diagnosed, which negatively impacts family, work, and overall participation in social roles and activities¹.

Word naming is impaired across all three clinical variants of PPA⁴.

Word-finding difficulties are most pronounced in the early stages of PPA in the semantic and logopenic variants. However, word naming problems are not a salient feature of the nonfluent/agrammatic variant until an advanced stage of disease progression^{5,6}. Targeting word naming training in PPA is of clinical relevance since difficulty finding words is among the chief early complaints². Research suggests that word naming training in PPA can lead to improved language outcomes⁷. However, gains following language training alone remain relatively small⁸. Therefore, researchers have utilized neuromodulation as an adjunctive technique to improve word-naming outcomes.

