When targeted to the inferior frontal gyrus (IFG), tDCS has been shown to improve word naming among individuals with word finding difficulties. The IFG is a key neural circuit for word naming^{28–30}. tDCS has been used in people with aphasia when it is paired with language training. Through both research^{26,31} and our clinical service²⁷, we have initial experience providing RS-tDCS paired with language activities to people living with aphasia. Among individuals with PPA, a recent meta-analysis strongly suggests that language training alongside tDCS exceeds the gains made through language training alone³², with the left IFG as a common neural target across naming studies. Furthermore, we have led the field in determining the feasibility of remotely-supervised tDCS (RS-tDCS) for individuals with PPA with differing typologies and various degrees of severity³¹. However, no study to date has systematically investigated the feasibility and acceptability of RS-tDCS paired with language training in PPA.

In the context of this progressive condition, the treatment goal is to extend the preservation of language functioning through the use of tDCS paired with word naming practice. In this open-label pilot study, we will measure the use of RS-tDCS in people with PPA. It is important for us to first demonstrate the acceptability and feasibility of the treatment. We will also pilot secondary clinical efficacy outcomes, to target personally relevant known words rather than attempting to restore access to forgotten words^{33,34}. Research suggests that recall is higher among those with PPA who have trained words of functional relevance compared to an untrained set of words^{33,35,36}. This study uniquely pairs the evidence from behaviorally-based language training studies in PPA alongside our established RS-tDCS protocol, allowing for determination of the clinical efficacy of tDCS as an adjuvant to PPA treatment.

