3.2 Secondary Objectives

Secondary objectives include exploratory analyses to evaluate the potential benefits of tDCS + word naming practice through change scores on language outcomes. This data will inform the power analysis for future study development.

4 Study Design and Endpoints

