4.1 Description of Study Design

This study will recruit n=30 PPA patients to receive 20x30 min sessions of active 2.0mA tDCS, combined with simultaneous word naming practice over a 4-week period.

All participants will have a remote consent/research screening visit, baseline visit, 20 tDCS treatment visits, and post-treatment assessment. All visits will be completed remotely using Zoom.

This will be a single site study at NYU Langone Health and will take place over a 2-year period.

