10.2 Statistical Hypotheses

This is a pilot test to assess the feasibility of RS-tDCS with word naming practice. The primary outcome measure will be percent compliance (e.g., at least 16/20 RS-tDCS sessions completed per participant).

In exploratory analyses, pre- and post- language assessment outcomes (trained and untrained words, QAB, BNT, COWAT) will be compared to determine if the intervention led to improved scores. Descriptive analyses will be completed to identify any trends in predicting those participants who are most likely to have improvement in language function at study end (e.g., age, gender, baseline function).

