10.3 Sample Size Determination

The primary objectives of this study are to: 1) establish feasibility of an RS-tDCS and word naming practice in an adult PPA population, and 2) collect preliminary efficacy data to inform a grant application and sample size calculations for a large controlled trial.

A total of 30 adult PPA participants will be enrolled in the study based on the estimated number of eligible patient contacts across the study period.

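### Sections 10.2 and 2.1 promise causal conclusions that a single-arm pre-post comparison cannot give, and the mean change should not become the tDCS effect in the next trial's sample size

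*Combined protocol and SAP*

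**What the plan says.** Section 4.1 describes one group of 30 patients "to receive 20x30 min sessions of active 2.0mA tDCS, combined with simultaneous word naming practice over a 4-week period". The Protocol Summary calls the design open label, and no participant receives naming practice without active tDCS.

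Section 10.2 (Statistical Hypotheses) says that, in exploratory analyses, pre and post scores on trained and untrained words, QAB, BNT and COWAT "will be compared to determine if the intervention led to improved scores". Section 2.1 goes further and presents the study as "allowing for determination of the clinical efficacy of tDCS as an adjuvant to PPA treatment".

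On the use of the data, section 3.2 says of the language change scores: "This data will inform the power analysis for future study development". Section 10.3 lists among its objectives to "collect preliminary efficacy data to inform a grant application and sample size calculations for a large controlled trial", and section 2.1 says the data will "inform a grant application to complete the next step of a randomized controlled trial". None of these places says which quantity is carried forward (mean change, SD, correlation or completion rate) or what the control arm of the later trial will receive.

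Section 10.4 is more restrained. It speaks of change after the intervention, plans descriptive analyses, names no test or interval, and computes change scores for compliant participants only.

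**The concern.** The phrase in 10.2 is a causal statement, and the design has no concurrent comparison to support it. The same tests are repeated after about four weeks, by staff and participants who know that treatment was given. A gain could come from retest, expectation, regression to the mean, or the programme itself. A loss could be natural decline that the programme slowed.

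The sentence in 2.1 is a further step away from the design. An adjuvant effect is tDCS plus training minus training alone, the same contrast that 2.1 uses when it cites a meta-analysis. Nobody in this trial receives training alone, and the protocol itself says that "Research suggests that word naming training in PPA can lead to improved language outcomes".

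Two things are at stake. The report could state a conclusion that the data cannot bear. The single-arm mean change could also be read as the effect of tDCS and used to size the controlled trial.

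**Working it through.** There is no planned calculation to reproduce. Section 10.3 sets the size by recruitment ("A total of 30 adult PPA participants will be enrolled in the study based on the estimated number of eligible patient contacts"), and the documents give no alpha, power, effect size or SD for either trial. Everything below marked as assumed is illustrative.

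**1. Can the pre-post comparison answer the question in 10.2?**

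Assume a two-sided 5% paired t test with n = 30 (10.4 names no test). Let the true tDCS effect be zero, and let training, retest and expectation together give a standardised gain g (assumed). The chance of a significant improvement is P(T > 2.045), where T is noncentral t with 29 df and noncentrality g√30.

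| g | g√30 | Chance of significant improvement |
|---|---|---|
| 0 | 0 | 2.5% |
| 0.2 | 1.10 | 18% |
| 0.3 | 1.64 | 36% |
| 0.5 | 2.74 | 75% |

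A modest shared gain is enough to produce an apparent success with no tDCS effect at all.

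**2. What if the mean change becomes the between-arm effect?**

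Assume a 1:1 trial, two-sided alpha 0.05, 80% power, SD 1, no dropout, and a carried-over standardised change d = 0.5.

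- Size per arm: n = 2(1.960 + 0.842)²/d² = 62.8, so 63.
- Let f be the share of the change that also occurs in controls. A negative f means that controls decline. The true difference is d(1 − f).
- Actual power: Φ(d(1 − f)√(n/2) − 1.960), with √(63/2) = 5.612.
- Size per arm needed for 80%: 62.8/(1 − f)², rounded up.

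| f | True difference | Actual power at 63 per arm | Per arm needed for 80% |
|---|---|---|---|
| −0.25 | 0.625 | Φ(1.548) = 94% | 41 |
| −0.10 | 0.550 | Φ(1.127) = 87% | 52 |
| 0 | 0.500 | Φ(0.846) = 80% | 63 |
| 0.10 | 0.450 | Φ(0.566) = 71% | 78 |
| 0.25 | 0.375 | Φ(0.145) = 56% | 112 |
| 0.50 | 0.250 | Φ(−0.557) = 29% | 252 |

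The powers are nearly the same for d = 0.3 (175 per arm) and d = 0.8 (25 per arm), so the choice of d matters little.

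**3. How precise is what can legitimately be carried forward?**

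The 95% limits for an SD, relative to its estimate, are √((n − 1)/χ²) at the 97.5% and 2.5% points.

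- n = 30: √(29/45.72) = 0.796 and √(29/16.05) = 1.344, so −20% to +34%.
- n = 24 (assumed number compliant): √(23/38.08) = 0.777 and √(23/11.69) = 1.403, so −22% to +40%.

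The second case matters because 10.4 restricts change scores to compliant participants and section 5.3 (Total Number of Participants and Sites) counts enrolment at consent, so the number analysed may be below 30. The mean is imprecise as well: an observed standardised change of 0.5 has a 95% CI of 0.12 to 0.88 at n = 30 and 0.07 to 0.92 at n = 24.

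**The case against.** The other side has several good points.

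- **The analysis is labelled exploratory, and 10.4 is descriptive.** True, and it limits the weight of the point. The label does not make a causal sentence valid, however, and 10.3 lists preliminary efficacy among its primary objectives. The wording of 10.4 is the better of the two, and 10.2 should follow it.
- **Section 10.2 does not single out tDCS.** Correct. The intervention there is the combined programme, as in 3.2, and only the sentence in 2.1 claims an effect of tDCS itself. Attribution to the combined programme still fails without a control.
- **Untrained words serve as a control list (7.1.1).** They are the items that participants did not choose, they are named by people under the same stimulation, and neither 10.2 nor 10.4 specifies a trained-versus-untrained contrast. At most they isolate practice on particular items, not tDCS.
- **To inform a power analysis need not mean using the mean change.** This stands. The SD, the correlation and retention would all satisfy the wording of 3.2 and 10.3.

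A reader might infer that the next trial will be underpowered. The documents do not support that. They do not say that the mean change will be the target difference, and they do not name the future comparator; sham plus naming practice is only one possibility. Section 2.1 calls gains from training alone relatively small and describes the disease as progressive. Controls might therefore share little of the change, or decline, and in the latter case the error runs the other way.

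**Conclusion.** The concern holds as a matter of wording and of what the data may be used for. As written, 10.2 promises a causal answer and 2.1 an adjuvant effect, and a single-arm, open-label design can deliver neither.

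The consequence for the later trial is conditional and two-sided. Power could fall from a planned 80% to between 71% and 29% if controls share 10% to 50% of the change, or rise to between 87% and 94% if they decline by 10% to 25% of it. These figures rest on assumed values of f, alpha, power and allocation, and on the mean change being taken as the between-arm effect. None of these is stated in the documents. What does not depend on them is that the single-arm mean change is not a usable estimate of the tDCS effect in either direction.

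The primary feasibility endpoint is untouched. The change is worth making because the secondary objective and the grant case rest on these scores.

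**What to change.** - **10.2:** replace the causal phrase with wording such as: *estimate within-participant change from baseline to treatment end (mean, SD, 95% CI) following the combined programme; this change is not attributable to tDCS.* Adding that it is also not proof of an effect of the programme would close the remaining gap.
- **2.1:** remove the claim that the study allows the adjuvant efficacy of tDCS to be determined.
- **3.2 and 10.3:** state that the SD of change (with confidence limits based on the number actually analysed), the pre-post correlation, and completion and dropout rates inform the next trial. State that the single-arm mean change is not used as the tDCS effect, and that the target difference will be justified separately.

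The cost is a few sentences in four sections and a more modest stated claim. Procedures, assessments, sample size and the feasibility endpoint do not change.

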10.3 Sample Size Determination

The primary objectives of this study are to: 1) establish feasibility of an RS-tDCS and word naming practice in an adult PPA population, and 2) collect preliminary efficacy data to inform a grant application and sample size calculations for a large controlled trial.

A total of 30 adult PPA participants will be enrolled in the study based on the estimated number of eligible patient contacts across the study period.

10.4 Description of Statistical Methods

For Objective 1, feasibility, individuals will be categorized as “compliant” based on percentage of study completion. Compliance with the interventions will be assessed by summarizing the distributions of numbers and proportions of

completed sessions. Descriptive analyses will be completed to identify any trends in predicting those participants who are most likely to be compliant (e.g., age, gender, baseline function).

For Objective 2, preliminary efficacy, we will convert performance at baseline and study end across study measures (QAB, BNT, COWAT, self-report questionnaires). Change in scores, indicating change following intervention, will be calculated for each compliant participant (defined as above). Descriptive analyses will be completed to identify any trends in predicting those participants who are most likely to have improvement in language function at study end (e.g., age, gender, baseline function) as well as corresponding degree of use of the RS-tDCS and word naming practice with magnitude of benefit.

11 Source Documents and Access to Source Data/Documents

Source data is all information, original records of clinical findings, observations, or other activities in a clinical trial necessary for the reconstruction and evaluation of the trial. Source data are contained in source documents. Examples of these original documents, and data records include: hospital records, clinical and office charts, laboratory notes, memoranda, subjects' diaries or evaluation checklists, recorded data from automated instruments, copies or transcriptions certified after verification as being accurate and complete, and subject files. It is acceptable to use CRFs as source documents. If this is the case, it should be stated in this section what data will be collected on CRFs and what data will be collected from other sources.

The study case report form (CRF) is the primary data collection instrument for the study. All data requested on the CRF must be recorded. All missing data must be explained. If a space on the CRF is left blank because the procedure was not done or the question was not asked, write "N/D". If the item is not applicable to the individual case, write "N/A". All entries should be printed legibly in black or blue ink. If any entry error has been made, to correct such an error, draw a single straight line through the incorrect entry and enter the correct data above it. All such changes must be initialed and dated. **DO NOT ERASE OR WHITE OUT ERRORS.** For clarification of illegible or uncertain entries, print the clarification above the item, then initial and date it.

Access to study records will be limited to IRB-approved members of the study team. The investigator will permit study-related monitoring, audits, and inspections by the IRB, the sponsor, government regulatory bodies, and University compliance and quality assurance groups of all study related documents (e.g. source documents, regulatory documents, data collection instruments, study data etc.). The investigator will ensure the capability for inspections of applicable study-related facilities.

Participation as an investigator in this study implies acceptance of potential inspection by government regulatory authorities and applicable University compliance and quality assurance offices.

12 Quality Assurance and Quality Control

QC procedures will be implemented beginning with the data entry system and data QC checks that will be run on the database will be generated. Any missing data or data anomalies will be communicated to the site(s) for clarification/resolution.

Following written SOPs, the monitors will verify that the clinical trial is conducted and data are generated, documented (recorded), and reported in compliance with the protocol, GCP, and the applicable NYU IRB regulatory requirements.

The investigational site will provide direct access to all trial related sites, source data/documents, and reports for the purpose of monitoring and auditing by the sponsor, and inspection by local and regulatory authorities.

13 Ethics/Protection of Human Subjects

13.1 Ethical Standard

The investigator will ensure that this study is conducted in full conformity with Regulations for the Protection of Human Subjects of Research codified in 45 CFR Part 46, 21 CFR Part 50, 21 CFR Part 56, and/or the ICH E6.

13.2 Institutional Review Board

The protocol, informed consent form(s), recruitment materials, and all participant materials will be submitted to the IRB for review and approval. Approval of both the protocol and the consent form must be obtained before any participant is enrolled. Any amendment to the protocol will require review and approval by the IRB before the changes are implemented to the study. All changes to the consent form will be IRB approved; a determination will be made regarding whether previously consented participants need to be re-consented.

13.3 Posting of Clinical Trial Consent Form

N/A

13.4 Participant and Data Confidentiality

Information about study subjects will be kept confidential and managed according to the requirements of the Health Insurance Portability and Accountability Act of 1996 (HIPAA). Those regulations require a signed subject authorization informing the subject of the following:

- What protected health information (PHI) will be collected from subjects in this study
- Who will have access to that information and why
- Who will use or disclose that information
- The rights of a research subject to revoke their authorization for use of their PHI.

In the event that a subject revokes authorization to collect or use PHI, the investigator, by regulation, retains the ability to use all information collected prior to the revocation of subject authorization. For subjects that have revoked authorization to collect or use PHI, attempts should be made to obtain permission to collect at least vital status (i.e. that the subject is alive) at the end of their scheduled study period.

Participant confidentiality is strictly held in trust by the participating investigators, their staff, and the sponsor(s) and their agents. Therefore, the study protocol, documentation, data, and all other information generated will be held in strict confidence. No information concerning the study or the data will be released to any unauthorized third party without prior written approval of the sponsor.

The study monitor, other authorized representatives of the sponsor, representatives of the IRB or pharmaceutical company supplying study product may inspect all documents and records required to be maintained by the investigator, including but not limited to, medical records (office, clinic, or hospital) and pharmacy records for the participants in this study. The clinical study site will permit access to such records.

The study participant's contact information will be securely stored at each clinical site for internal use during the study. At the end of the study, all records will continue to be kept in a secure location for as long a period as dictated by local IRB and Institutional regulations.

Study participant research data, which is for purposes of statistical analysis and scientific reporting, will be transmitted to and stored at NYU Langone Medical Center. This will not include the participant's contact or identifying information. Rather, individual participants and their research data will be identified by a unique study identification number. The study data entry and study management systems used by clinical sites and by NYU Langone Medical Center research staff will be secured and password protected. At the end of the study, all study databases will be de-identified and archived at the NYU Langone Medical Center.

14 Data Handling and Record Keeping

14.1 Data Collection and Management Responsibilities

Data collection is the responsibility of the clinical trial staff at the site under the supervision of the site PI. The investigator is responsible for ensuring the accuracy, completeness, legibility, and timeliness of the data reported.

All source documents should be completed in a neat, legible manner to ensure accurate interpretation of data. Black ink is required to ensure clarity of reproduced copies. When making changes or corrections, cross out the original

entry with a single line, and initial and date the change. DO NOT ERASE, OVERWRITE, OR USE CORRECTION FLUID OR TAPE ON THE ORIGINAL.

Copies of the electronic CRF (eCRF) will be provided for use as source documents and maintained for recording data for each participant enrolled in the study. Data reported in the eCRF derived from source documents should be consistent with the source documents or the discrepancies should be explained and captured in a progress note and maintained in the participant's official electronic study record.

The self-reported questionnaires will be administered through REDCap survey function providing access to secure online questionnaires that can be completed from any browser. All study data collected through REDCap will be printed and stored in locked cabinet only accessible to the research staff at [name].

